Given the high volume of PCI, its high cost, its lack of effect on survival and the potential for alternative treatments including exercise and risk reduction in PCI candidates, the current proposal is termed “**PCI Alternative Using Sustained Exercise**” (PAUSE). **The primary aim of PAUSE is to employ non-invasive methods to determine whether patients randomized to exercise intervention have greater improvement in coronary function and anatomy compared to those randomized to PCI.** Both groups will receive optimal medical management. We will also compare health care costs, symptoms, quality of life, and clinical outcomes between the two groups. At baseline and one year after randomization, patients will undergo an assessment of physical activity patterns and fitness using standardized questionnaires and maximal cardiopulmonary exercise testing (CPX). Patients will also undergo evaluation of coronary function and anatomy with positron emission tomography combined with computed tomographic angiography (PET/CTA). PET will be used to measure myocardial perfusion. CTA will be used to evaluate anatomical progression of atherosclerotic disease based on a qualitative scoring system of coronary artery calcium. The combination of PET/CTA provides information that previously could only be obtained invasively using coronary flow wires and invasive x-ray angiography. This will permit a non-invasive way to evaluate both functional and anatomical adaptations to exercise. Our overall objective is to demonstrate the utility of a non-invasive technology to document the efficacy of exercise therapy as an alternative treatment strategy to PCI for coronary lesions.

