*Measurement of myocardial blood flow will be performed at baseline and 1-year in all subjects. Intravenous  $^{13}\text{NH}_3$  will be used as the flow tracer and serial imaging with PET will be performed (83,84). Measurements will be performed at baseline, and after pharmacologic stress with dipyridamole (85). A 20-minute transmission scan will be acquired first for correction of photon attenuation (86). After the first intravenous injection of  $^{13}\text{NH}_3$  (15 to 20 mCi), resting serial transaxial images will be acquired in a sequence consisting of 12 image frames of 10 seconds, 2 frames of 30 seconds, and 1 frame of 900 seconds. Forty-five minutes later, 0.56 mg/kg of dipyridamole IV will be infused over 4 minutes (85).  $^{13}\text{NH}_3$  (15 to 20 mCi) will be injected 4 minutes after the end of the dipyridamole infusion, and serial images will be recorded in the same sequence. Myocardial blood flow at rest and following dipyridamole infusion will be expressed as ml flow/100 g/min. The myocardial perfusion reserve will be calculated as the ratio of the myocardial blood flow during stress (e.g. after dipyridamole) and the myocardial blood flow at rest.*

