Comparisons of coronary lesions progression or regression of stenosis and change in calcified and noncalcified plaque area) and functional flow reserve between the two groups at baseline and 1 year post-randomization using CT with contrast will be a secondary outcome. For analysis of anatomy (12), a scoring system will used to quantify disease progression or regression. Stenoses with <10% change in diameter reduction will be classified as unchanged ( $\pm 0$ ). A difference  $\geq 10\%$  between baseline and follow-up will be graded as progression (+1) and a negative difference  $\geq 10\%$  will be graded as regression (-1). Any lesion that necessitates intervention by PCI or bypass surgery will be assigned a grade of +3. Progression from subtotal occlusion to total occlusion (99% to 100%) and spontaneous recanalization will not be graded. In the culprit lesion, an asymptomatic in stent restenosis <50% will be calculated as no change ( $\pm 0$ ). An in-stent restenosis of  $\geq 50\%$  will be rated as progression (+1). An in-stent stenosis  $\geq 50\%$  that required intervention will be classified as progression (+3). A single variable is calculated per patient by adding the grades assigned to the separate stenosis. For analysis of calcified and non-calcified plaque burden (90), the coronary arteries will be divided into 12 segments according to the American Heart Association classification (33). For every coronary artery segment

(identified via side branches) the presence of calcified or noncalcified plaque, both, or neither will be determined using axial and multiplanar reformatted images. To measure plaque volume in each coronary segment, contiguous 1 mm thick cross sectional images of the coronary arteries will be rendered and displayed with a fixed setting (700-HU window, 200-HU level). Plaque areas will be manually traced and volume calculated by multiplying area and slice increment. In the distal segments, analysis of plaque will be limited to the proximal 20 mm. For comparison of calcium scores, total calcium and per artery calcium scores will be compared.

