### ***Statistical Analysis Plan***

***Key Question #1:*** Does exercise training favorably alter coronary anatomy and function as determined by non-invasive imaging techniques?

***Statistical Analysis, Key Question #1.*** Myocardial blood flow using PET at rest and following dipyridamole infusion will be expressed as ml flow/100 g/min. The primary outcome, myocardial perfusion reserve, will be calculated as the ratio of the myocardial blood flow during stress (e.g. after dipyridamole) and the myocardial blood flow at rest. Differences within and between groups will be assessed using repeated measures ANOVA, with group (exercise vs. PCI) and test (baseline vs. 1-year) as factors. Post-hoc procedures will be performed using the Bonferonni method.

***Key Question #2:*** Can a program of exercise therapy improve outcomes (exercise capacity, symptoms, repeat hospitalizations, and quality of life) in patients with CAD that are equivalent or superior to PCI?

Statistical Analysis, Key Question #2. These secondary outcomes will include changes in peak  $VO_2$  and other cardiopulmonary exercise test responses (including  $VO_2$  at the ventilatory threshold, exercise time, and heart rate recovery), quality of life measures, and lipid panels. Paired tests will be used (paired t-test or Wilcoxon signed rank test) to compare continuous variables between groups at baseline. Differences between groups after the 1-year study period will be assessed by repeated measures ANOVA, with group (exercise vs. PCI) and test (baseline vs. 1-year) as factors. Post-hoc procedures will be performed using the Bonferroni method.

**Key Question #3:** Will exercise training reduce costs as compared to standard PCI after 1-year?

Statistical Analysis, Key Question #3. Comparison of costs will be made for the individual level change scores using the intervention net-costs (intervention delivery minus healthcare expense cost-savings). Cost effectiveness of the intervention will be defined by the primary outcome at the patient level. That is, changes from baseline in individual global myocardial perfusion reserve using PET at 1-year will be used to calculate the effect. Differences in costs between groups will be assessed using ANOVA.

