### **Sample Size Estimates**

*Sample size estimates are based on our primary endpoint, change in global myocardial blood flow reserve from baseline using pharmacologic stress with dipyridamole, and applying variance in myocardial blood flow reserve measured by PET published previously in subjects with coronary artery disease (71,77,78). We anticipate that the overall change in the primary endpoint will be approximately 15%; this is based on previous measurements of coronary blood flow reserve using PET comparing sedentary and fit subjects cross-sectionally (77), after exercise training (78), and risk reduction interventions such as smoking cessation (96). We also anticipate that these changes will parallel the well-documented changes in exercise capacity with training in subjects with CAD (i.e. mean change in peak  $VO_2 \approx 15\%$ ) (18,19,24). Given a standard deviation of myocardial flow reserve in similar populations of 0.20 ml/g/min both at baseline and after treatment with a pre-post correlation of 0.65 (calculated from the data in reference 96), the standard deviation of the change in myocardial blood flow is 0.167. We want to detect a 15% change (absolute change of  $0.15 \times 0.9$  or 0.135) so the standardized effect size (absolute value of difference in group values for mean change divided by the standard deviation) is about 0.81. Using a 2-sided significance level of 0.05 and 80% power, 25 subjects in each group will be needed to complete the protocol.*

We anticipate that there will be a 20% dropout rate, which is typical of that in the cardiac rehabilitation literature and in accordance with our previous experience. Thus, our target enrollment will be 32 subjects in each group. The dropout rate may be lower given that compliance tends to be better in research studies compared to clinical practice, and that the subjects will receive continuous monitoring, follow-up, and encouragement to remain physically active. *Dropouts will not be included in the statistical analyses (97).*

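### Dropouts are excluded from the analyses but never defined, and no analysis by assigned arm is stated, so the primary comparison can be read as completers versus completers

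*Combined protocol and SAP*

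**What the plan says.** The primary aim in the Statement of the Problem is to determine "whether patients randomized to exercise intervention have greater improvement in coronary function and anatomy compared to those randomized to PCI", which is a comparison of groups as randomised.

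The Statistical Analysis Plan, Key Question #1, gives the method: "Differences within and between groups will be assessed using repeated measures ANOVA", with group and test occasion as factors. It names no analysis set and no missing-data method, and it does not say that subjects are analysed in the arm assigned.

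The only rule on who is analysed is in Sample Size Estimates: "Dropouts will not be included in the statistical analyses (97" (the number is a literature citation). The same section states that "25 subjects in each group will be needed to complete the protocol" and gives the source of the allowance: "We anticipate that there will be a 20% dropout rate, which is typical of that in the cardiac rehabilitation literature". It adds: "The dropout rate may be lower given that compliance tends to be better in research studies compared to clinical practice". Enrolment is set at 32 per group.

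Three other places bear on the rule:

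- PET Methods: "Measurement of myocardial blood flow will be performed at baseline and 1-year in all subjects".
- Monitoring Phone Calls: exercise subjects who miss their goals receive encouragement and closer monitoring. Removal is not mentioned.
- CT Imaging, on the secondary anatomy score: "Any lesion that necessitates intervention by PCI or bypass surgery will be assigned a grade of +3". No matching rule is given for the primary PET outcome.

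**The concern.** The plan does not say what makes a subject a dropout. It could mean stopping exercise, missing the 1-year scan, withdrawing, not receiving the assigned PCI, or having PCI later in the exercise arm. The choice decides who enters the primary analysis.

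If stopping the programme counts, subjects whose 1-year PET could be obtained are left out because of something that happened after randomisation. What remains compares exercise completers with PCI completers, which is a different question from the stated aim and no longer has the protection of randomisation. If the term stays open, it could also be fixed after results are known. With 64 subjects, a few discretionary exclusions matter.

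**Working it through.** **1. The plan's own figures.** Inputs from Sample Size Estimates: SD 0.20 at each time point, pre-post correlation 0.65, target 0.15 × 0.9 = 0.135, two-sided 5% level, 80% power, 20% dropout.

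- SD of change = √(0.20² + 0.20² − 2 × 0.65 × 0.20 × 0.20) = 0.167.
- n per arm (normal approximation) = 2 × [0.167 × (1.960 + 0.842) / 0.135]² = 24.0, or 24.1 with the unrounded SD, which rounds up to 25. A two-sample t-test with 25 per arm has 80% power.
- Enrolment = 25 / 0.80 = 31.25, rounded up to 32.

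The sample size reproduces. The issue is the analysis set. At 20% loss, 32 × 0.8 = 25.6 per arm remain and 64 × 0.2 = 12.8, about 13 subjects, are left out.

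**2. Which reading does the text support?**

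- *Stopping the programme:* sizing on subjects who complete; a rate taken from cardiac rehabilitation; a remark that better compliance may lower it.
- *No 1-year scan:* PET scheduled in all subjects; encouragement for missed goals; the same 20% in both arms, although the PCI arm has no training programme to stop; weekly calls to all subjects.

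Neither reading is settled.

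**3. Possible bias if subjects are excluded.** Let f be the share of an arm excluded, and k the gap in mean change between that arm's completers and its excluded subjects, in SDs. The completers' mean differs from the whole arm's mean by f × k × 0.167. The documents give no value for k, so 0.5 to 1 is an assumption, as is selection in one arm only. The standard error with 25 per arm is 0.167 × √(2/25) = 0.0472. Type I error is the chance of p < 0.05 when the true difference between the arms as randomised is zero (two-sample t, 48 df).

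| f (one arm only) | k | Difference off by | Share of 0.135 | Type I error |
|---|---|---|---|---|
| 0.20 | 0.5 | 0.017 | 12% | 6.4% |
| 0.20 | 1 | 0.033 | 25% | 10.7% |
| 7/32 | 0.5 | 0.018 | 14% | 6.7% |
| 7/32 | 1 | 0.037 | 27% | 11.8% |

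The sign depends on which arm is affected and on whether the excluded subjects did worse or better. With the same f and k in both arms, the two shifts cancel: bias 0, type I error 5.0%.

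**4. Power when analysed by assigned arm.** Assume all 32 per arm are scanned, and exercise completers change by 0.135 more than the PCI arm.

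- Subjects who stop respond like completers: difference 0.135, power 89%.
- 7 of 32 exercise subjects change like the PCI arm: difference 25 × 0.135 / 32 = 0.105, power about 70% (68% by simulation).

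**The case against.** The strongest reply is that dropout here means loss to follow-up. The evidence is in step 2: PET in everyone, retention of subjects who miss goals, and the same allowance in an arm with no programme to stop. On that reading little is lost, because a two-occasion repeated measures ANOVA uses only subjects with both values. A model that adds subjects with only a baseline scan would contribute little. This stands as a possible reading, and it is why bias is a risk and not a demonstrated error. It does not make the rule safe, because the sizing and the compliance argument point the other way.

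The definition might also lie in the source cited for the rule or in the Appendix I flow chart, neither of which was available. A rule that decides the primary analysis set should still be stated in the plan.

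Three stronger inferences are tempting and are not supported:

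- **That the result will be biased in favour of exercise.** The visit burden does differ (about 38 against 8), but no passage shows one-sided exclusion or how excluded subjects would fare.
- **That power by assigned arm would fall to half or below if the PCI arm also improves and subjects who stop do not.** With a PCI-arm change of 0.09 or 0.18, this needs exercise completers to gain 0.225 or 0.315, that is 25% or 35% of 0.9. The plan anticipates about 15%, and the training study it cites reported 20%.
- **That the cost sections contradict the exclusion rule.** They describe tracking each patient's utilisation. Tracking more patients than are analysed is not a contradiction, although the cost analysis set does need stating.

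**Conclusion.** The point holds as a defect in the stated analysis rule. The plan excludes an undefined group and never commits to analysis by assigned arm. One reasonable reading discards obtainable primary-outcome data and replaces the randomised comparison with completers against completers. The other gives a complete-case analysis with little PET data lost, but still without a missing-data sensitivity analysis.

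The tabulated sizes are conditional on k between 0.5 and 1 and on selection in one arm only. They show that the ambiguity could matter, not that it will. The sample size arithmetic is correct. This should be settled before any outcome comparison is made, because it governs the primary analysis and costs little to correct.

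**What to change.** Replace the exclusion sentence with one primary rule: all randomised subjects with a 1-year PET are analysed in the arm assigned, regardless of adherence, crossover or later revascularisation. State that the 1-year PET already scheduled will be sought in subjects who stop the programme.

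Then:

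- Define dropout as having no 1-year PET, separately from stopping the assigned treatment, and report numbers and reasons by arm.
- Add, as labelled sensitivity analyses, a missing-data model using baseline reserve with one missing-not-at-random scenario, and the completers analysis.
- State which subjects enter the cost comparison and which enter the cost-effectiveness analysis. The latter needs both a cost and a PET change for each subject.
- Restate power for 64 subjects with its assumption: about 89% if subjects who stop respond like completers, about 70% if 7 of 32 exercise subjects change like the PCI arm.

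The cost is SAP wording and the effort of bringing subjects back for a scan already planned; routine care at the same facility for both groups helps. The downside is a possibly smaller expected effect, and so lower stated power. No extra enrolment or additional scans are required.

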### **Timeline**

Identification and recruitment of eligible subjects will take place during the initial months of the study, and exercise training will begin as soon as eligibility is confirmed and baseline testing completed. We anticipate that all subjects will be recruited during the first 1.5 years of the study and that the project will take 3 years to complete. We do not expect much delay in getting started as there is an established exercise training research program at the VA Palo Alto Medical Center. Statistical analyses, reports, and manuscript writing will begin during year 3. An outline of the study timeline and tasks is presented in Appendix V.

## **Collaboration**

All studies will be performed in the Cardiology Division at the Palo Alto VAHCS, where there are laboratories for electrocardiography, echocardiography, and exercise testing currently in use. All training will be performed in the Palo Alto VAHCS Rehabilitation Research & Development Center, on the campus of the Medical Center. The training facility is currently being used for an ongoing NIH SCCOR project (“Exercise Therapy in Abdominal Aortic Aneurysm Disease”), where both dynamic and resistance exercise equipment are in place, and will be used for the current study. All exercise testing and training procedures will be performed by the study personnel; collaboration with the Nuclear Medicine Department will be necessary to perform the PET/CTA scans. Collaboration with the Cardiac Catheterization Laboratory will be necessary to recruit potential subjects for the study. Drs. [name] and [name] will collaborate with [name], the nurse coordinator, and other study personnel to address any clinical concerns that may arise.

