**Cardiopulmonary Exercise Testing.** Peak  $VO_2$  will be determined at baseline and after 6 months and 1 year on a treadmill using an individualized ramp protocol with collection of continuous ventilatory gas exchange responses. A thorough clinical history, medications and risk factors will be recorded prospectively at the time of baseline exercise testing using computerized forms that include standard definitions of clinical conditions and exercise responses. In accordance with standard practice at the Palo Alto VAHCS, prior to exercise testing, patients complete a questionnaire to estimate exercise capacity; the questionnaire is used to individualize the exercise protocol which allows most patients to reach maximal effort within the recommended range of 8 to 12 minutes (58). We previously observed that this protocol provides the closest relation between measured and estimated metabolic equivalents (METs) (59). Patients will be discouraged from using the handrails for support. Medications will not be changed or stopped prior to testing. A 12-lead electrocardiogram, heart rate, and blood pressure responses will be monitored throughout the exercise test and recovery period. Ventilatory gas exchange measurements will be obtained continuously at rest, throughout exercise, and during 5 minutes of recovery. All subjects will be encouraged to give a maximal effort, and the Borg 6-20 scale will be used to quantify subjective effort (60). Standardized clinical indications for stopping will be used. ST-segment depression will be measured visually at the J junction, and slope will be determined over the following 60 ms and classified as upsloping, horizontal, or downsloping. Ventricular tachycardia will be defined as three or more consecutive premature ventricular contractions, and *frequent* premature ventricular contractions will be defined as 10% or more of the total ventricular contractions. Blood pressure will be measured manually, and exercise capacity will be measured directly using ventilatory gas exchange techniques. The exercise tests will be performed, analyzed, and reported according to a standardized protocol and utilizing a computerized database (61).

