Commercially available software (Emory tool box) will be used to quantitatively analyze PET myocardial perfusion images. Stress and rest images will be divided according to the 17-segment model (87). The software will define whether ischemia is present and the location and extent of the ischemia relative to the specific myocardial territory (88). The software compares normalized relative radiotracer uptake in reconstructed slices against normal data files. Relative radiotracer uptake on PET images is displayed either as polar plots or bull's eye plots, or as circumferential count distribution profiles. The size of myocardial perfusion defects will be expressed as percentage of the left ventricle. In general, defect extent will be defined as small (5 to 10% of the left ventricle), medium (15 to 20% of the left ventricle), or large (>20% of the left ventricle). Defect severity will be defined as mild, moderate, or severe based on myocardial tracer content compared against normalized data (89). Qualitative interpretation by Drs. [name] and [name] will be used to determine if there were technical issues with regard to processing that impair analysis by the software. *Drs. [name] and [name] will oversee all PET/CTA scans and their interpretation, and they will be blinded to study group when reviewing the images.*

**CT Imaging.** After myocardial perfusion imaging, all patients will undergo calcium scoring and CT angiography (120 kv; 500 mA). First, a prospectively gated low dose sequential CT scan of the heart will be performed for coronary calcium detection and quantification. Patients with pre-scan heart rates above 70 beats per minute will receive intravenous beta-blocker therapy (5 to 15 mg metoprolol tartrate) immediately prior to the CT scan if no contraindications are present. Additionally, 0.04 mg of sublingual nitroglycerin will be administered for coronary dilatation to every patient prior to the scan. ECG-pulsing for radiation dose reduction will be used in all patients. Synchronized to the ECG, CT data sets will be retrospectively reconstructed in mid- to end-diastolic phases and additional phases if needed for optimal coronary artery visualization. Standard reconstruction parameters for slice thickness, field of view, and convolution kernel will be used. For post-processing and image interpretation, the images will then transferred to an external designated workstation (Advantage Workstation, GE).

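### Exercise tests are run by the team that delivers the training, with no blinding stated, so peak VO2, exercise time and ventilatory threshold are open to arm-dependent effort or reading

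*Combined protocol and SAP*

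**What the plan says.** On who does the work, the Collaboration section states: "All exercise testing and training procedures will be performed by the study personnel".

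On how the tests are run, the Cardiopulmonary Exercise Testing paragraph under Study Procedures says peak VO2 "will be determined at baseline and after 6 months and 1 year on a treadmill using an individualized ramp protocol". It continues: "All subjects will be encouraged to give a maximal effort, and the Borg 6-20 scale will be used to quantify subjective effort". It also contains safeguards: "exercise capacity will be measured directly using ventilatory gas exchange techniques", and "The exercise tests will be performed, analyzed, and reported according to a standardized protocol and utilizing a computerized database".

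On blinding, the only statement is in PET Methods, about the two physicians who oversee PET/CTA interpretation: "they will be blinded to study group when reviewing the images".

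On use of the results, the Statistical Analysis Plan for Key Question #2 lists change in peak VO2 first among the secondary outcomes, followed by other test responses that include VO2 at the ventilatory threshold, "exercise time, and heart rate recovery". The arms are compared by repeated measures ANOVA on baseline and 1-year values.

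**The concern.** Peak VO2 and treadmill time depend on how hard the patient pushes, and that depends partly on the person urging them on. A team that delivers one of the two treatments, and expects it to do better, runs the tests that compare them. If exercise-arm patients are pushed a little harder at follow-up, or stay on longer for staff they know well, the extra effort would be counted as a training gain over PCI.

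VO2 at the ventilatory threshold is submaximal, so encouragement matters much less there. Its exposure is different: the documents do not say how the threshold is determined, or that whoever determines it is unaware of arm and visit.

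Key Question #2 asks whether exercise is as good as or better than PCI. An artefact favouring exercise would bear directly on that answer. Sample Size Estimates also expects the perfusion changes to run in parallel with the change in peak VO2, so peak VO2 is likely to be read as support for the primary result.

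**Working it through.** **1. The plan's own figures.** The sample size rests on PET perfusion reserve alone (Sample Size Estimates).
- SD of change = 0.20 × √(2 × (1 − 0.65)) = 0.167.
- Effect size = (0.15 × 0.9) / 0.167 = 0.135 / 0.167 = 0.81.
- n per arm, normal approximation on unrounded values (effect size 0.807) = 2 × (1.960 + 0.842)² / 0.807² = 24.1, rounded up to 25. The t-test version at 0.81 gives 24.9, also 25.
- Enrolment = 25 / (1 − 0.20) = 31.25, rounded up to 32.

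These reproduce the stated 25 and 32. Nothing in this point changes them.

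**2. Can the bias enter the comparison?**
- Screening Process and Informed Consent puts the baseline exercise test before randomization, so arm cannot influence it.
- The 6-month and 1-year tests come after randomization, and no text conceals the arm from whoever runs or reads them.
- Arm-dependent effort or reading would therefore sit in the follow-up value only. It would pass in full into the change score and would not cancel. The stated model uses the 1-year test; the 6-month test is exposed in the same way if reported.
- Contact with staff is unequal: Subject Burden gives about 38 hospital visits for the exercise arm and about 8 for the PCI arm.

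**3. Is it controlled anywhere?** No section separates testers from trainers, scripts the encouragement, blinds the derivation of peak VO2 or threshold, or specifies an objective criterion of effort. Gas exchange is recorded throughout each test, so the respiratory exchange ratio can be obtained without a new measurement.

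**4. How much could it matter? (illustration only)** The documents give neither an SD for peak VO2 nor a size of bias. Let b be an assumed bias towards exercise, in SDs of the change score. With 25 per arm, no true difference and a two-sided 0.05 t-test on change (equivalent to the group-by-test interaction with two time points), the statistic is noncentral t with 48 degrees of freedom and noncentrality b × √(25/2) = 3.54b.

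| Assumed b | Noncentrality | Chance of a significant result |
|---|---|---|
| 0 | 0 | 5% |
| 0.1 | 0.35 | 6% |
| 0.2 | 0.71 | 11% |
| 0.3 | 1.06 | 18% |
| 0.5 | 1.77 | 41% |

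A bias of 0.1 SD is nearly harmless; 0.3 SD more than triples the false-positive rate. The documents do not show where in this range, if anywhere, the trial would fall.

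**The case against.** The plan is not careless here. Encouragement is directed at every subject, stopping indications are standardized, capacity is measured rather than estimated, and conduct and reporting follow a standard protocol whose cited source may hold more than the text shows. All of that stands. It makes the measurement accurate and reduces loose practice, but it does not equalize effort between arms when the tester knows the arm.

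A reader might go further than the documents allow in four ways.
- *The same person trains and tests each patient.* This is not stated. Study personnel is a team, and the sentence in Collaboration mainly distinguishes in-house work from work needing Nuclear Medicine. The same section places exercise testing laboratories in the Cardiology Division and training in the Rehabilitation Research & Development Center. What stands is that one team does both and no rule keeps the roles apart.
- *No objective effort measure will be used.* The text supports only that none is specified. The list of exercise test responses is open-ended.
- *A definite share of the expected 15% gain in peak VO2 would be artefact.* The 15% in Sample Size Estimates is a change expected with training, cited in support of the perfusion assumption. It is not an exercise-minus-PCI difference, and no bias estimate is available to set against it.
- *The trial's main result is compromised.* It is not. The primary outcome is PET perfusion reserve, and its readers are blinded.

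It is also fair to say that tester masking is fragile when patients know whether they had PCI or a year of training. That limits what masking can achieve at the test, but not what coded reading can achieve afterwards.

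**Conclusion.** The point holds as an uncontrolled risk of bias in secondary outcomes. Peak VO2 and exercise time are exposed through effort, and VO2 at the ventilatory threshold through unblinded determination. A direction favouring exercise is plausible, because the team delivers that arm and hypothesizes its benefit, but the documents cannot establish it. The size is unknown; the table above only shows what assumed biases would do. The conclusion rests on the absence of any stated blinding, role separation or objective effort criterion for these tests, and would weaken if a laboratory procedure outside these documents provides them. The change is worth making because it is cheap. It does not bear on the validity of the primary analysis.

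**What to change.** Amend the Cardiopulmonary Exercise Testing paragraph to state the following.
- Peak VO2 and the ventilatory threshold are derived from coded files with arm and visit removed.
- The 6-month and 1-year tests use a fixed encouragement script. Where existing staffing allows, they are run by a team member who does not train that patient and is not told the arm.
- Peak respiratory exchange ratio, taken from the gas exchange already recorded, is reported by arm and visit as an objective check on effort.
- The comparison using all tests remains the main one. Any analysis limited to tests reaching a pre-set ratio is labelled descriptive, because it selects on a variable measured after randomization and so loses the protection of the randomized comparison. It would also leave fewer than the roughly 25 completers per arm.

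The cost is file coding and some scheduling constraint. The documents give no staffing numbers, which is why the separate tester is conditional. Patients may still reveal their arm. No visit, measurement or treatment is added and the sample size is unchanged. The script and tester rule should be in place before the first follow-up test, since arm-dependent effort cannot be removed afterwards.
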